9.2 Follow-up of AEs and SAEs

After the initial AE or SAE report, the investigator is required to proactively follow each participant at subsequent visits/contacts. All SAEs that occur after the first VTP-850 administration will be followed until resolution, stabilisation, the event is otherwise explained, or the participant is lost to follow-up (as defined in [Section 7.3](#)). Further information on follow-up procedures is provided in [Appendix 3](#).

9.3 Regulatory Reporting Requirements for SAEs

- Prompt notification by the investigator to the sponsor of an SAE is essential so that legal obligations and ethical responsibilities towards the safety of participants and the safety of a trial intervention under clinical investigation are met.

The sponsor has a legal responsibility to notify both the local regulatory authority and other regulatory agencies about the safety of a trial intervention under clinical investigation. The sponsor will comply with country-specific regulatory requirements relating to safety reporting to the regulatory authority, IECs/IRBs, and investigators.

An investigator who receives an individual case safety report describing an SAE or other specific safety information (e.g., summary or listing of SAEs) from the sponsor will review and then file it along with the IB and will notify the IRB/IEC, if appropriate according to local requirements.

Individual case safety reports must be prepared for suspected unexpected serious adverse reactions (SUSARs) according to local regulatory requirements and sponsor policy and forwarded to investigators as necessary.

9.4 Disease-Related Events and/or Disease-Related Outcomes Not Qualifying as AEs or SAEs

Progression of prostate cancer including radiographic evidence of progression will be captured as an endpoint and does not need to be reported as an AE or SAE.

9.5 Adverse Events of Special Interest

The following events have been identified as adverse events of special interest (AESI) for the purpose of expedited reporting to Sponsor during the conduct of this trial::

- any cardiac event

- shortness of breath / dyspnoea
- abnormal cardiac investigation or examination

If a cardiac event is reported, blood should be taken for assessment of troponin T and C-reactive protein (CRP) and the participant should undergo an ECG and echocardiogram at the earliest opportunity along with any other appropriate assessments as determined by the Investigator.

10 PHARMACOKINETICS

Pharmacokinetic parameters are not evaluated in this trial.

11 STATISTICAL CONSIDERATIONS

The statistical analysis plan (SAP) will be finalised prior to database lock, and it will include a more technical and detailed description of the statistical analyses described in this section. This section is a summary of the planned statistical analyses of the most important endpoints including primary and key secondary endpoints.

11.1 Statistical Objectives

The primary objective is to demonstrate that VTP-850 has a reasonable safety and tolerability profile. No formal hypothesis will be tested.

The secondary objectives include evaluating the presence and durability of PSA response to VTP-850. Estimated response rates and durability may be used for power and sample size purposes in subsequent trials.

11.1.1 Multiplicity Adjustment

The analyses associated with this trial are primarily descriptive in nature, and multiplicity adjustments have not been specified.

11.1.2 Analysis sets

- The intent-to-treat analysis set (full analysis set) will consist of all participants who are enrolled into the trial and who received at least one dose of VTP-850
- The safety analysis set will consist of all participants who receive at least one dose of VTP-850 (data will be summarised according to the dose levels and regimens actually received)
- The per-protocol analysis set will consist of all participants in the safety analysis set who received the correct trial intervention and who had no major protocol deviations that would potentially bias the trial's analyses
- The immunogenicity analysis set will consist of all participants who have available immunogenicity data to evaluate the immunogenicity endpoints and do not have any major protocol deviations that would impact the results of the immunological analysis

Assignment of participants to the analysis sets (and whether any participant or specific data from a participant will be excluded) will be determined at the pre-database-lock Data Review meeting.

11.2 Statistical Analyses

11.2.1 General Considerations

Most analyses will be descriptive in nature. Unless stated otherwise, continuous variables will be summarised using descriptive statistics (number of participants, mean, standard deviation, median, minimum and maximum values), and the number and percentage of participants will be presented for categorical variables. Data will be summarised by trial cohort and, where appropriate, overall. Immunogenicity and efficacy data may have additional statistical analysis, which will be detailed in the trial's SAP.

The SAP will describe and account for the occurrence of and extent of missing data and its possible impact on the trial analysis.

11.2.2 Primary Endpoint Analysis

Safety data will be summarised descriptively. Adverse Events are defined as those occurring after trial intervention administration.

11.2.2.1 Adverse Events

All AEs will be listed, including the verbatim description and the Medical Dictionary for Regulatory Activities (MedDRA) preferred term (PT) and system organ class (SOC).

All AEs will be summarised by SOC and PT over the course of AE follow-up, as well as during the 28-day period following each administration of VTP-850. The incidence of AEs will be based on the numbers and percentages of participants with events. AEs will be further summarised by severity and relationship to trial intervention.

An overall summary of AE incidence will also be presented by trial cohort and overall to include the number and percentage of participants with at least one: AE, treatment-related AE, Grade 3 to Grade 5 AE, death, SAE, treatment-related SAE, AE leading to trial intervention discontinuation and AE leading to trial discontinuation.

Narratives will be written for any deaths, other SAEs, AESIs, AEs leading to trial intervention discontinuation and AEs leading to trial discontinuation.

11.2.2.2 Laboratory Safety Tests

Severity grading using CTCAE Version 5.0 will be assigned to laboratory safety values where applicable. Laboratory results in reported units and International System of Units (SI) units will be listed, including high and low flags, severity grades where applicable, the corresponding normal range and clinical significance.

Safety laboratory tests summaries will be based on results in SI units. Absolute and change from baseline results, including the worst change for each parameter for each participant, will be summarised using descriptive statistics.

Treatment-emergent, out-of-range results with the corresponding severity grade, normal ranges, baseline results and clinical significance will be listed separately. Shift tables of the CTCAE grades will be used to show changes from baseline at each timepoint and the worst change in each participant. The number of participants showing shifts of at least 2 severity grades will be summarised.

The number of participants with treatment-emergent clinically significant safety laboratory test results and safety laboratory test results of Grade 3 or 4 will be summarised.

11.2.2.3 Vital Signs

Absolute and change from baseline vital sign results, including the worst change for each variable for each participant will be summarised using descriptive statistics. Treatment-emergent, out-of-range results with the corresponding normal ranges, baseline results and clinical significance will be listed separately. The number of participants with treatment-emergent, clinically significant results will be summarised.

11.2.3 Secondary Endpoint Analyses

11.2.3.1 PSA Response to VTP-850

The number, proportion, and 90% confidence interval (CI) of participants with a PSA response, defined as $\geq 50\%$ reduction in serum PSA compared to baseline and measured twice consecutively, will be summarised by timepoint and overall. This will be further broken down by whether the participants had prior radical prostatectomy or prior external beam radiation. The maximum PSA reduction from baseline will be summarised, as well as by whether participants had prior radical prostatectomy, external beam radiation or brachytherapy.

11.2.3.2 Durable PSA Response to VTP-850 at Month 8

The number, proportion and 90% CI of participants with a durable PSA response at Month 8 will be summarised, among all participants and among those with a response by Month 6. Durable PSA response is defined as having follow-up through Month 8 and a confirmed PSA response without having PSA progression (i.e., an increase relative to nadir of $\geq 25\%$ and an absolute increase of 0.2 ng/mL or more) on or before Month 8. This will be further summarised by whether the participants had prior radical prostatectomy, external beam radiation or brachytherapy.

11.2.3.3 Duration of PSA Response to VTP-850

Among those participants who experienced a PSA response, the duration of PSA response, defined as the time from first dose of VTP-850 to the date of PSA progression, will be summarised (n, median, interquartile range, minimum, maximum) and presented using a

Kaplan-Meier plot. Participants whose PSA response is ongoing upon the completion of follow-up will be censored at the time of their last follow-up visit with a non-missing PSA evaluation. An additional analysis will evaluate duration of PSA response, defined as the time from observation of PSA reduction of at least 50% to the date of PSA progression.

This endpoint will be further summarised by whether the participants had prior radical prostatectomy, external beam radiation or brachytherapy.

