|----------------------|--|--|
| | 
To assess the MFS and TTM of all participants
 | 
 • MFS is defined as the time from date of first dose of VTP-850 until metastatic disease by conventional imaging (CT/MRI and/or technetium-99 bone scan) or death from any cause, whichever occurs first • TTM is defined as the time from date of first dose of VTP-850 until metastatic disease by conventional imaging (CT/MRI and/or technetium-99 bone scan) 
Note that MFS and TTM events do not include local progression events, e.g., progression in pelvic lymph nodes below the aortic bifurcation
 |

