11.2.3.4 Metastasis-Free Survival and Time to Metastases

The duration of MFS, defined as the time from first dose of VTP-850 to detection of metastatic disease or all-cause mortality, will be summarised (n, median, interquartile range, minimum, maximum) and presented using a Kaplan-Meier plot. Participants who have survived without development of metastatic disease by the end of follow-up will be censored at the time of their last follow-up visit with an evaluable assessment of metastatic disease.

The duration of TTM, defined as the time from first dose of VTP-850 to detection of metastatic disease, will be summarised (n, median, interquartile range, minimum, maximum) and presented using a Kaplan-Meier plot. Participants who have not developed metastatic disease by the end of follow-up will be censored at the time of their last follow-up visit with an evaluable assessment of metastatic disease.

These endpoints will be further summarised by whether the participants had prior radical prostatectomy, external beam radiation or brachytherapy. These endpoints will be further summarised for participants who experienced a PSA response.

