11.2.3.5 Time to Start of ADT for Participants with PSA Response

Among those participants who experienced a PSA response, the time to initiation of ADT treatment (or when they have met the criteria to initiate ADT) will be summarised (number of participants, median, interquartile range, minimum, maximum) and presented using a Kaplan-Meier plot. Responders who have not started ADT or met the criteria to start ADT by the end of follow-up will be censored at the time of their last follow-up visit.

This endpoint will be further summarised by whether the participants had prior radical prostatectomy or external beam radiation. This endpoint will be further summarised for participants who experienced a PSA response.

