6.6.2. Secondary Efficacy Analysis

6.6.2.1. PSA Response to VTP-850

The number, proportion and 90% confidence intervals (CI) of participants with a confirmed PSA response, defined as a $\geq 50\%$ reduction in serum PSA compared to baseline and measured twice consecutively, at least 2 weeks apart, will be summarized by timepoint (using visit windows defined in Section 5.1) and overall for each treatment group using the EES. The proportion at each time point will present the participants who have the 1st (if confirmed at least 2 weeks later) measurement where the $\geq 50\%$ reduction in serum PSA has been met compared to baseline. Percentage change in PSA will be calculated as $100 \times (\text{PSA value (ng/ml) at visit } i - \text{PSA value at baseline}) / (\text{PSA value at baseline})$. The 90% CIs will be calculated using Jeffrey's confidence limits. The maximum percentage change in PSA from baseline will be summarized continuously by treatment group. A waterfall plot of maximum percentage change in PSA from baseline will be produced by treatment group with bars of the waterfall plot produced using different colours to represent prior radical prostatectomy or definitive external beam radiation (Yes, No). Per cohort, a spaghetti plot will display each participant's percentage change in PSA (e.g. each patient's baseline measurement will display as 100%) by the number of days since the day 1 dosing visit. On each participant's line, a marker will indicate the study day each dose occurred.

Example of this calculation of confirmed PSA response are displayed in Table 7 and Table 8.

Table 7: Calculation of PSA Response Example

Participant	Timepoint	Study Day	PSA Value (ng/mL)	PSA change from baseline	PSA absolute change from nadir	PSA percent change from nadir
1	Baseline	1	1.5			
1	Day 29	29	1.6	6.67%		
1	Day 57	57	1.0	-33.33%		
1	Day 64	64	0.9	-40.00%		
1	Month 4	122	0.8	-46.67%		
1	Month 5	153	0.2	-86.67%		
1	Month 6	164	0.2	-86.67%		
1	Month 7	215	0.3	-80.00%	0.1	50.00%
1	Month 8	246	0.3	-80.00%	0.1	50.00%
1	Month 9	271	0.5	-66.67%	0.3	150.00%

- Responder = Yes
- First observed PSA response = Month 5

- PSA progression (Defined in Section **Error! Reference source not found.**) = Month 9 (since there's a $\geq 25\%$ increase from PSA nadir AND an absolute increase of ≥ 0.2 ng/mL)
- Durable PSA response at Month 8 (Defined in Section 6.6.2.2) = Yes (since a confirmed PSA response has occurred and the criteria for PSA progression has not been met)

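### The four responder-only endpoints run from first dose, so duration of response counts pre-response time, and responder MFS, TTM and time to ADT include time guaranteed free of death, detected metastasis and ADT start

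*Protocol*

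**What the plan says.** All four endpoints share one time origin.

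- **Duration of response** (Protocol 11.2.3.3): "the duration of PSA response, defined as the time from first dose of VTP-850 to the date of PSA progression", among responders, with a Kaplan-Meier plot. The same section adds: "An additional analysis will evaluate duration of PSA response, defined as the time from observation of PSA reduction of at least 50" per cent, again ending at PSA progression.
- **MFS and TTM** (Protocol 11.2.3.4): "The duration of MFS, defined as the time from first dose of VTP-850 to detection of metastatic disease or all-cause mortality", and "The duration of TTM, defined as the time from first dose of VTP-850 to detection of metastatic disease". Then: "These endpoints will be further summarised for participants who experienced a PSA response". The responder results are secondary endpoints. The exploratory objective is "To assess the MFS and TTM of all participants".
- **Time to ADT** (Protocol 11.2.3.5): "Among those participants who experienced a PSA response, the time to initiation of ADT treatment". The origin is given in the synopsis and Section 3: first dose, ending at the earlier of ADT start or meeting criteria for it.

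Responder status arises later. It needs a fall of at least 50% on two consecutive PSA values at least 2 weeks apart, and the first post-baseline PSA is on Day 29. Follow-up stops at new therapy or unequivocal metastasis (Protocol 4.1). Men without a response by Month 6 leave, except that a man awaiting confirmation may stay after discussion with the Medical Monitor (Protocol 4.1.4).

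The SAP covers Phase 1 only and leaves these endpoints to a Phase 2 SAP not yet written (SAP 2.1, 2.2.2). Neither document gives a landmark, delayed-entry or response-onset version of responder MFS, TTM or time to ADT.

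**The concern.** Selecting a group by something that happens after the clock starts has two effects here.

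For duration of response, the main definition adds the wait for a response to the length of the response. A slow responder gets a longer duration than a fast one whose response lasted equally long. The text also does not say that progression must come after response, so a rise from nadir before the response could, as written, end the duration before it began. The SAP's worked examples leave the change-from-nadir columns blank until after response, which suggests the intended order, but no rule states it.

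For MFS, TTM and time to ADT, a man who dies, has metastasis detected or starts ADT before his response is confirmed cannot be counted as a responder. Everyone who is counted was therefore free of those events up to confirmation.

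The results will be used. Protocol 2.1 relies on these endpoints to describe the quality of responses. Section 11.1 says durability estimates may inform power and sample size in later trials. Section 11.3 puts all secondary endpoints into an interim analysis for planning future trials.

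**Working it through.** The documents give no event count, power or expected median for these endpoints, so there is no planned figure to reproduce. The response-rate figures in Protocol 11.4 do reproduce (P(X≥20 | 125, 0.20) = 0.893; P(X≥4 | 25, 0.20) = 0.766), but they concern a different endpoint.

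**1. SAP worked examples (SAP 6.6.2.1).** In Table 7 the first dose is on Day 1, "First observed PSA response = Month 5" falls on Day 153, and progression is on Day 271.

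- From first dose: 271 − 1 = 270 days. From response: 271 − 153 = 118 days. Ratio 270/118 = 2.29.
- Before any response: 153 − 1 = 152 days; 152/270 = 56%.
- The two confirming values are on Days 153 and 164, and 164 − 153 = 11 days, short of the SAP's own 2-week rule. Starting at Day 164 (next value Day 215) gives 271 − 164 = 107 days and a ratio of 270/107 = 2.52, so the point is unaffected.
- In Table 8, response is on Day 122 with no progression by Day 282: 281 against 160 days of censored time. The difference of 121 days is 121/281 = 43%.

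**2. PSA schedule (SAP 2.5; Protocol Tables 1 and 2).** Target days, ignoring visit windows; Day 1 to Day 720 is 719 days.

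| First fall of ≥50% | Days before response | Earliest scheduled confirmation ≥14 days later | Days to confirmation |
|---|---|---|---|
| Day 29 | 28 | Day 57 | 56 |
| Day 57 | 56 | Day 91 | 90 |
| Day 64 | 63 | Day 91 | 90 |
| Day 91 | 90 | Day 120 | 119 |
| Day 120 | 119 | Day 150 | 149 |
| Day 150 | 149 | Day 180 | 179 |
| Day 180 | 179 | Day 210 | 209 |

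Time before response is 28 to 179 days (28/719 = 4%; 179/719 = 25%). Time to confirmation is 56 to 179 days if confirmed by Month 6. The last row (179 and 209 days) needs the pending-confirmation allowance. Without it, the latest first fall is Day 150, or 149 days.

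**3. Effect on median duration.** If response starts at t months and lasts a median of m months, the first-dose median is t + m and the ratio is (t + m)/m. The values of m are assumptions: with m = 6 and t = 3 it is 9/6 = 1.5. Over m from 3 to 12 and t from 0.92 to 5.9, the ratio runs from 1.08 (12.92/12) to 2.97 (8.9/3).

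**4. Effect on MFS, TTM and time to ADT.** Assumptions: exponential event times with median M, events detected when they occur, response unrelated to prognosis, a responder event-free at his first fall, and first falls spread evenly over the seven visits above. A simulation of 400,000 men gives:

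| Assumed M (months) | Responder median from first dose | Responder median from response | 24-month rate, all | 24-month rate, responders |
|---|---|---|---|---|
| 12 | 15.2 | 12.0 | 25% | 30% |
| 24 | 27.1 | 24.0 | 50% | 55% |
| 36 | 39.1 | 36.0 | 63% | 67% |

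With one fixed onset t, the responder rate is exp(−(ln 2/M)(24 − t)). For M = 24 that is 51% at t = 0.92 and 59% at t = 5.9, against 50% for all men. Response has no effect in this model, so the whole gap comes from the choice of origin. Timed from response, the gap disappears.

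**The case against.** A reader might infer that time before response is event-free by construction for all four endpoints. The documents do not support that. PSA progression does not end follow-up, so it can precede a response. The fault in duration of response is that it counts pre-response time, not that the event was impossible. Likewise, meeting criteria for ADT does not end follow-up, and the endpoint definition does not state those criteria. The guarantee is strict only for death, detected metastasis and actual ADT start.

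A reader might also infer that onset-based duration is missing. It is planned in Section 11.2.3.3, so both figures should be reported. What remains is which one is the named endpoint.

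The strongest objection concerns metastases. Protocol Table 2 puts the first scheduled on-trial scan at Month 6, so a responder confirmed by then has had no scheduled metastasis assessment. Only deaths and unscheduled imaging could have excluded anyone, and the effect on MFS and TTM is mainly a shift of origin. The simulated gaps assume immediate detection and overstate what scan-detected metastases would show. Early ADT is also limited by entry criterion 9, which requires no plan to start ADT for at least 4 months.

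Finally, the analyses are descriptive, no test of responders against others is planned for these endpoints, and first dose is an ordinary origin in a single-arm trial. That holds for all treated men. It is not neutral in a subset chosen by later response. Nor does the all-participant curve correct it: non-responders leave at Month 6, so later follow-up comes almost entirely from responders.

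**Conclusion.** The concern holds with those limits. The main duration of response includes 28 to 179 days before any response existed (149 at most if confirmation must fall by Month 6), and progression is not required to follow response. Responder MFS, TTM and time to ADT carry 56 to 179 days guaranteed free of death, detected metastasis and ADT start, or up to about 209 if a pending confirmation is allowed. No version of those three endpoints corrects for this.

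The day counts rest on the scheduled visits. The Table 7 ratio of 2.29 is one hypothetical man in an SAP that excludes these endpoints; it illustrates the effect and does not estimate a typical inflation. The medians and 24-month rates rest on assumed event medians and on response being unrelated to prognosis.

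This should be changed before the Phase 2 SAP is final, mainly because the durations may be used to plan later trials.

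**What to change.** - **Duration of response:** make time from the first of the two confirming PSA values to subsequent PSA progression the main definition, and say that progression must follow response. Keep the first-dose version as supportive.
- **Responder MFS, TTM and time to ADT:** add to the Phase 2 SAP a version from confirmed response or from a Month 6 landmark. If a landmark is used, state how a man with a pending confirmation is classified.
- **Interpretation:** state that the first-dose responder curves are not to be read against the all-participant curve as evidence of benefit.
- **Consistency:** align the definitions in the synopsis, Section 3 and Sections 11.2.3.3 to 11.2.3.5. First dose can stay as the origin for all-participant MFS and TTM.
- **SAP Table 7:** correct the example so that its confirming values meet the 2-week rule.

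No new data, visits or participants are needed. The cost is a protocol amendment, with the ethics approval that Appendix 1 requires, plus text in an SAP that still has to be written. Reported durations become shorter, and a landmark drops the few responders with earlier events. Precision is limited whichever origin is used: at a 20% response rate, 0.20 × 125 = 25 responders are expected.
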